### **E.2. Statistical specification**

Our primary analytic approach is an analysis based on the intent-to-treat principle that compares outcomes for those randomized into the treatment group to those who were randomized into the control group.

Our models account for time-stable heterogeneity across individuals and treatment sites using random intercepts for each individual enrolled in the study, for each time period during which surveys are collected, and for the county from which their qualifying OCFS case originated. These random effects adjust for correlation induced by repeated measurements of individuals over time, time period effects, and clustering of outcomes within counties.

Our regression models for outcome variable  $y$  take the following general form:

$$\mu = E(y|T, X) = \alpha_i + \delta_j + \gamma_k + \beta T_i + c_j T_i + \theta X_{ij}$$

$$\begin{pmatrix} \alpha \\ \delta \\ \gamma \end{pmatrix} \sim N(0, \Sigma)$$

Where  $T$  indicates selection into the treatment group,  $X$  is a matrix of demographic characteristics,  $i$  indicates an individual participant,  $k$  indicates county of residence at the time of study enrollment,  $j$  indicates survey time period,  $\alpha$  is a vector of individual-level intercepts,  $\delta$  is a vector of time period intercepts,  $\gamma$  is a vector of county-level intercepts,  $\beta$  is the time-stable component of the treatment effect,  $c$  is a vector of time-varying components of the treatment effect, and  $\theta$  is a vector of coefficients for demographic predictors.

The relationship between the treatment and outcomes of interest may vary as a function of time. We treat temporal relationships as potentially nonlinear, and model the relationship between time, treatment, and outcomes of interest using a series of time-period intercepts. We estimate a unique intercept for each treatment period as well as an interaction between treatment status and treatment period to capture time-varying effects of treatment.

For all continuous (additive index) outcomes with a roughly symmetric distribution, we treat the outcome as following a linear model where

$$y \sim N(\mu, \sigma^2)$$

For all binary outcomes, we treat the outcome as following a Bernoulli model

$$y \sim \text{Bernoulli}(p)$$

$$E(p|T, X) = \text{logit}^{-1}(\mu)$$

And for all count outcomes and additive index outcome with a non-symmetric distribution, we treat the outcome as following a negative binomial model

$$y \sim \text{NB}(\mu, \psi)$$

$$E(y|T, X) = e^{\mu}$$

where  $\psi$  is a shape parameter.

The average treatment effect is identified as

$$\text{ATE} = E(y|T = 1, X) - E(y|T = 0, X)$$

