## **D. Data, Study Sample, Outcomes, and Other Variables**

### **D.1. Data and Study Samples**

The study sample will be recruited from the population of eligible households in Monroe, Onondaga, and Westchester counties, New York. We will randomly select 50 households per county into the treatment arm, and 100 households per county into the control arm.

Data will be obtained from two sources:

1) A web-based survey for all study participants at baseline, at 6 months after treatment begins, at 12 months after treatment begins, and at 18 months after treatment begins (6 months after treatment ends). This survey will collect information on caretaker and child demographic, health, behavioral, educational, and social characteristics. All variables will be collected at baseline. We will repeat data collection for all time-varying variables at each post-baseline wave of the survey.

2) OCFS administrative records linked to the study participants and their children using the DOB and name of the study participant and all minor children in the participant's household. Data will be provided by OCFS as family-specific and child-specific counts of a series of events related to child maltreatment reports and agency interventions.

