### **D.2. Planned Outcomes**

#### **Primary Outcomes:**

Primary outcomes are measured as event counts between baseline and 18 months after the beginning of study interventions using OCFS administrative data. We will treat all primary outcome events as integer count variables, with the exception of preventive services which will be treated as binary (services delivered / no services delivered). In the event that observed study outcomes are rare in the sample, we will treat primary outcomes as binary (occurred / did not occur) instead of treating rare outcomes as event counts.

The primary study outcomes (and variable class) are:

- Investigative Track OCFS maltreatment cases: event count
- Family Assessment Response (FAR) track OCFS cases: event count
- Total OCFS cases: event count as sum of investigative track and FAR track cases
- Indicated OCFS maltreatment investigations: event count
- Substantiated OCFS maltreatment investigations: event count
- OCFS foster care placements: event count
- Preventive services for families at risk of foster care: binary

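### E.2 offers only a repeated-survey model, which is not identified term by term for primary outcomes that are single baseline-to-18-month values

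*Combined protocol and SAP*

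**What the plan says.** On the primary outcomes, D.2 states: "Primary outcomes are measured as event counts between baseline and 18 months after the beginning of study interventions using OCFS administrative data". Six are counts and one (preventive services) is binary. If events turn out to be rare, "we will treat primary outcomes as binary (occurred / did not occur) instead of treating rare outcomes as event counts". Only the secondary outcomes in D.2 are described as collected at each of the four survey waves.

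E.2 then gives one equation for any outcome y. Its linear predictor contains alpha_i (participant), delta_j (survey period), gamma_k (county), a treatment effect beta, period-specific treatment terms c_j T_i, and covariates. The text describes "random intercepts for each individual enrolled in the study, for each time period during which surveys are collected", and for county. It says these effects "adjust for correlation induced by repeated measurements of individuals over time", among other purposes. The distributions are assigned by variable type: "For all binary outcomes, we treat the outcome as following a Bernoulli model", and "for all count outcomes and additive index outcome with a non-symmetric distribution, we treat the outcome as following a negative binomial model". Between them these two statements cover all seven primary outcomes.

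E.2 closes with "The average treatment effect is identified as", followed by the difference between E(y|T=1,X) and E(y|T=0,X). Neither alpha_i nor a period is mentioned there. E.3 keeps both treatment terms and multiplies them by a race coefficient d_l. E.4 refits every model by MCMC. No section gives a form for a single-interval outcome or says that the administrative counts will be divided by survey period.

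**The concern.** The index j in E.2 is a survey period, but an administrative total from baseline to 18 months has no survey period. A model built to handle repeated measurements is therefore assigned to outcomes that are measured once. Several of its terms then have nothing in the data to estimate them, and the plan does not say which ones drop out.

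At stake is which number is reported. E.2 places alpha_i inside the quantity it calls E(y|T,X), under logit and log links. On those links, a treatment difference computed at alpha_i = 0 is not the same as one averaged over alpha_i, and the gap depends on the SD of alpha_i. If the data cannot determine that SD, a conditional odds ratio or an ATE at alpha_i = 0 reflects the fitting routine or the prior. The exposure is greatest for rare outcomes, which D.2 says will become binary.

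**Working it through.** The plan gives no event rate, effect size or power figure, so there is nothing of its own to reproduce. Every risk, mean and SD below is an assumption. From the documents come 3 counties x 50 = 150 treatment households, 3 x 100 = 300 control households (450 in total), and the two-sided 0.05 level.

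**1. Which fixed terms can be estimated.** With one record per household, take four columns: constant, period, T, period x T. The period column equals the constant and period x T equals T, so the rank is 2 of 4. Only (intercept + delta_1) and (beta + c_1) are estimable. With 3 or 4 periods (1,350 or 1,800 rows) the rank is 6 or 8, that is, one level per arm per period. The form therefore suits the repeated survey outcomes.

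**2. The SD of alpha_i, binary outcome.** Write s for the SD. The observable risk in arm T is p_T = integral of expit(m_T + s u) phi(u) du. Without covariates, any s can be matched exactly by re-solving m_T. For assumed risks of 30% and 20%, s = 0, 1 and 2 fit equally well, with conditional odds ratios of 0.583, 0.532 and 0.430. Covariates help very little. In 60 simulated trials for each risk pair in step 3 (150 versus 300, county and one covariate fitted), the maximised log-likelihood across s = 0 to 3 varied by a median of 0.04 to 0.07 (largest 0.56).

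**3. Effect on the ATE, binary outcome.** Solve m_T for each assumed pair of risks, then compute expit(m_1) - expit(m_0). For example, at 5% versus 3.5% and s = 2, m_0 = -4.422 and m_1 = -4.895. The risks at alpha_i = 0 are then 1.19% and 0.74%, a difference of about -0.44 points.

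| Assumed risks (control vs treatment) | ATE at alpha_i = 0, in points, for s = 0, 1, 2, 3 | ATE averaged over alpha_i |
|---|---|---|
| 30% vs 22% | -8.0, -8.4, -8.6, -7.5 | -8.0 at each s |
| 10% vs 7% | -3.0, -2.4, -1.3, -0.6 | -3.0 at each s |
| 5% vs 3.5% | -1.5, -1.05, -0.44, -0.14 | -1.5 at each s |

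In the same simulations, the averaged ATE moved across s by a median of about 0.1 points (largest 0.5). In a separate set of 40 trials per risk pair with s estimated freely, the estimate mostly ran to a search bound (0.02 or 4.95). The median ATE at alpha_i = 0 was -0.08 points against -1.9 averaged (5% vs 3.5%), and -0.9 against -3.4 (10% vs 7%).

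**4. Counts.** Assume a control mean of 0.5 and a rate ratio of 0.7, so the averaged ATE is 0.5 x (0.7 - 1) = -0.150. Because the mean is exp(m + s^2/2), the ATE at alpha_i = 0 is -0.150 x exp(-s^2/2): -0.150, -0.132 and -0.117 at s = 0, 0.5 and 0.71. In 60 simulated trials the fitted shape psi rose to compensate (medians 1.09, 1.81, 4.39). The log-likelihood spread had a median of 0.62 (largest 2.47), so the two sources of overdispersion are weakly separable. The median averaged ATE moved only from -0.146 to -0.139.

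**5. The significance decision.** In 40 simulated trials per risk pair (120 in all, binary), with s fixed at 0 to 3, the likelihood-ratio p-value for treatment moved by a median of 0.002 to 0.014. It crossed 0.05 in none of the 120.

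**6. E.3 with one record.** The treatment part becomes d_l (beta + c). Multiplying every d_l by a constant and dividing (beta + c) by it leaves the fit unchanged, so only the product is identified.

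**The case against.** The best defence is that E.2 presents its equation as a general form and the reduction is nearly mechanical. Once the redundant period terms are absorbed, what remains is treatment, county, covariates and a superfluous alpha_i, close to the model one would write anyway. A reader might infer that the primary analysis cannot be carried out at all. The documents do not support that, since beta + c remains estimable. What stands is that the plan does not state the reduction and that alpha_i does not drop out unaided.

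Second, the ATE conditions only on T and X. Read literally, that favours averaging over alpha_i, and nothing in the plan says to set it to zero. This is a fair point: the large shifts in step 3 need the alpha_i = 0 reading together with an SD of 2 to 3. The ambiguity remains because E.2 equates E(y|T,X) with the inverse link of a predictor that contains alpha_i.

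Third, the administrative counts might be split by survey period, in which case E.2 would fit. D.1 and D.2 do not exclude this, but neither says it, and D.2 describes one interval.

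Two further readings go too far. D.1 says "Data will be provided by OCFS as family-specific and child-specific counts of a series of events", from which one might infer a child-level analysis that ignores family clustering. No such analysis is proposed, and household randomisation and the participant index i strongly imply family level. One might also infer that the MCMC refit in E.4 lets the prior set the treatment effect. The data inform beta + c, and the prior governs only how that sum is divided.

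**Conclusion.** The specification is wrong as written for all seven primary outcomes: the only stated model is not identified term by term when each family contributes one 18-month value. The mismatch follows from D.2 and E.2 alone and needs no assumed rate.

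Its numerical consequence depends on what is reported. For the total effect and an averaged ATE it is small, and for binary outcomes the simulations suggest that the decision at P < 0.05 would rarely change. Decision stability was not simulated for counts. For conditional coefficients, or an ATE at alpha_i = 0, the result rests on an SD the data do not determine, and for rare binary outcomes the reported effect could shrink several-fold. These sizes rest on assumed risks, means and SDs. The finding does not show that the trial's conclusions would be wrong.

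**What to change.** In E.2, state that each primary outcome is analysed with one baseline-to-18-month record per family, by negative binomial regression (logistic if binary) on treatment, county and baseline covariates, without alpha_i, delta_j or c_j T_i. State that the ATE is the difference between predictions under T=1 and T=0, averaged over the sample.

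Use the same reduced form in E.4. In E.3, for these outcomes, replace the d_l multiplier with a treatment-by-race interaction, giving one treatment coefficient per race group, so that the model is identified. Keep the repeated-measures model for the survey outcomes.

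If interval-split administrative counts are intended instead, say so, define the intervals, keep alpha_i and average the ATE over it.

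The cost is SAP wording only, with no new data and no loss of information.

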## Secondary outcomes:

Secondary outcomes are related to child and family health, well-being, and stability. All outcomes are measured during each wave of survey data collection [baseline, 6 months, 12 months, 18 months]. For all measures derived from additive indices, we will treat measures as continuous. If the empirical distributions of additive indices are roughly symmetric, we will treat them as continuous real numbers. If the empirical distributions of additive indices are skewed, we will treat them as non-negative integers.

- Parental self-reported general health (19 physical health items derived from SF-36): items scored following RAND Corporation SF-36 scoring instructions for included questions. Additive index
- Mental health (Kessler 10 plus) Each item is scored from one 'none of the time' to five 'all of the time'. Scores of the 10 items are then summed, yielding a minimum score of 10 and a maximum score of 50. Additive index
- Stress and coping (Perceived Stress Scale - 4): Each item is scored from "never" to "all of the time" on a 5-point scale. Scores of 4 items are then summed, yielding a minimum score of 0 and a highest score of 16. Higher scores are correlated to more stress. Additive index
- Family dynamics and parenting (CHAOS): Each item is scored "yes" or "no". Scores of the items are then summed. The higher the score the higher the level of environmental chaos in the home. Additive index
- Parental Stress Scale: 18-item questionnaire assessing parents' feelings about their parenting role, exploring both positive aspects (e.g. emotional benefits, personal development) and negative aspects of parenthood (e.g. demands on resources, feelings of stress). Each item is scored on a 5-point Likert scale. Parental stress scores range from 18 to 90, with lower scores indicating lower levels of parental stress. Additive index
- Food insecurity: In the past four weeks, did you worry that your household would not have enough food? Binary
- Adult Hope Scale: 12 items scored on an 8-point ordinal scale. Additive index
- Child missed medical care: Parental yes/no report of any child in home with missed medical care in preceding 6 months. Binary
- Child truancy: Parental report of day of missed school for each child in the home aged 6-17 in the preceding 6 months. Ordinal [no missed days; 1-3 days; 4-6 days; 7-10 days; 11 or more days; child not enrolled in school]

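### For the continuous secondary survey outcomes, E.2's single person intercept forces equal correlation and equal variance across the four waves, so standard errors for within-person treatment contrasts can be wrong in either direction

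*Combined protocol and SAP*

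**What the plan says.** Section E.2 describes the person-level term this way: "Our models account for time-stable heterogeneity across individuals and treatment sites using random intercepts for each individual enrolled in the study". Further random intercepts for survey period and county follow. The claim made for them is "These random effects adjust for correlation induced by repeated measurements of individuals over time".

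In the model equation, alpha_i carries no time index. For symmetric additive indices ("For all continuous (additive index) outcomes with a roughly symmetric distribution, we treat the outcome as following a linear model where") the residual variance is a single sigma^2, not indexed by wave. The treatment effect is split into a time-stable part, beta, and time-varying parts, c_j. The c_j enter through "an interaction between treatment status and treatment period to capture time-varying effects of treatment".

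The repeated measurements are the secondary outcomes in D.2: "All outcomes are measured during each wave of survey data collection [baseline, 6 months, 12 months, 18 months". The primary outcomes have a different structure: "Primary outcomes are measured as event counts between baseline and 18 months after the beginning of study interventions using OCFS administrative data".

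No random slope, serial correlation, wave-specific variance or robust standard error is stated. The joint matrix Sigma for alpha, delta and gamma does not supply one, because these terms are indexed by person, period and county. It cannot make within-person correlation depend on the time between waves. The sensitivity analyses in E.4 re-estimate the same models under different priors.

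**The concern.** A person intercept plus independent residuals of constant variance is compound symmetry. Scores 6 months apart and scores 18 months apart are assumed equally correlated, and the spread is assumed the same at all four waves. Repeated measures of distress, stress or financial well-being may well correlate less as the interval grows. If so, the fitted model applies the average correlation to every pair of waves. It then understates the standard error of contrasts between distant waves and overstates it for adjacent ones.

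The terms at risk are the c_j, which E.2 uses to describe how the effect changes over time. A change in effect from baseline to 18 months would be declared too often. A change from 12 to 18 months, one natural way to ask whether gains last after payments stop, would be tested with too little power. The plan states the adjustment as achieved and names no fallback if the assumption fails.

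**Working it through.** The plan gives no correlation, standard error or power figure for the survey outcomes, so there is nothing to reproduce. The check asks how far the model's standard errors depart from the true ones under stated assumptions.

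**Inputs from the documents**
- Four waves: baseline, 6, 12 and 18 months (D.2).
- 150 treated and 300 control families over three counties ("We will randomly select 50 households per county into the treatment arm, and 100 households per county into the control arm", D.1).
- Two-sided 0.05. E.5 states this for the primary outcome; it is applied here to the survey outcomes.

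**Assumptions**
- Complete data unless stated, outcome SD 1, counties and covariates left out, separate means for each arm and wave.
- Correlation patterns: autoregressive, rho^k for waves k steps apart; mild decay, 0.65/0.60/0.55 at 6/12/18 months; and exact compound symmetry.

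**Formulas.** Four waves form six pairs: three 6 months apart, two 12 months apart, one 18 months apart. With balanced data the random-intercept model settles on the mean pairwise correlation

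r = (3 rho_1 + 2 rho_2 + rho_3) / 6.

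For a treatment contrast between two waves k steps apart:
- true SE = sqrt[2(1 - rho_k)(1/150 + 1/300)] = sqrt[0.02(1 - rho_k)]
- model SE = sqrt[0.02(1 - r)]
- type I error = 2[1 - Phi(1.96 x model SE / true SE)]

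**Worked case, rho = 0.7**
- r = (2.1 + 0.98 + 0.343)/6 = 0.5705, so model SE = sqrt(0.02 x 0.4295) = 0.093 for every pair of waves.
- Baseline to 18 months: true SE = sqrt(0.02 x 0.657) = 0.115. Model/true = 0.81; type I error 11.3%.
- Baseline to 12 months: model/true = sqrt(0.4295/0.51) = 0.92; type I error 7.2%.
- Adjacent waves, including 12 to 18 months: true SE = sqrt(0.02 x 0.300) = 0.077. Model/true = 1.20; type I error 1.9%. A contrast that should have 80% power has Phi(2.80 - 1.96 x 1.196) = 0.68.

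**Range**

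| Assumed correlation | r | 18 months vs baseline: model/true SE, type I | Adjacent waves: model/true SE, type I |
|---|---|---|---|
| Compound symmetry 0.6 | 0.600 | 1.00, 5.0% | 1.00, 5.0% |
| Mild decay 0.65/0.60/0.55 | 0.617 | 0.92, 7.1% | 1.05, 4.0% |
| Autoregressive 0.5 | 0.354 | 0.86, 9.2% | 1.14, 2.6% |
| Autoregressive 0.7 | 0.571 | 0.81, 11.3% | 1.20, 1.9% |
| Autoregressive 0.85 | 0.768 | 0.77, 12.9% | 1.24, 1.5% |
| Autoregressive 0.9 | 0.842 | 0.76, 13.4% | 1.26, 1.4% |

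A separate generalised least squares calculation with sandwich variances agrees for the patterns it covered (all but autoregressive 0.9). A simulation of 4,000 trials at rho 0.6, 0.7 and 0.8 gave 9.7%, 11.5% and 12.1% for baseline to 18 months, and 2.3%, 1.8% and 2.0% for 12 to 18 months. An unstructured covariance gave 4.3-5.6%.

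**Arm difference at one wave (beta + c_j).** Its SE depends on the variance at that wave, not on the correlation between waves. With equal variances and complete data, model/true is 1.00 and type I error 5.0% in every pattern. With 30% dropout by 18 months, completely at random, it is 4.8-5.8%. The average over the three post-baseline waves has 5.4-5.9% under autoregressive decay with complete data.

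**Unequal variances.** Let the SD be 1.0, 1.1, 1.2 and 1.3 over the waves, with constant correlation 0.6. The model's pooled variance is (1 + 1.21 + 1.44 + 1.69)/4 = 1.335, so its SD is 1.155. At 18 months model/true = 1.155/1.3 = 0.89, and the single-wave test has type I error of 8.2%.

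**The case against.** The strongest reply is that the plan's own effect measure is the arm difference, E(y|T=1,X) - E(y|T=0,X). At a given wave this is beta + c_j, whose standard error is correct under equal variances. No section names a baseline-to-18-month or 12-to-18-month contrast as a test, and no reference wave for c_j is given. Persistence after payments stop could be read from the 18-month arm difference instead. This stands. A reader might infer that all time-varying treatment effects carry wrong error bars, and the calculations do not support that. What remains is that E.2 does make the c_j part of the analysis without saying which contrast will be reported, and the arm difference is itself exposed if the spread changes by wave.

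Second, the error is conditional. Under exact compound symmetry there is none, and the documents give no correlations. A reader might take 11% as the expected error rate; it belongs to one assumed pattern, and mild decay gives 7.1%. This also stands.

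Third, a person intercept is a conventional choice and does adjust for repeated measurement. That is so, but the adjustment is complete only under an assumption the plan neither states nor tests.

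Fourth, the calculations are for Gaussian outcomes. In the logistic and negative binomial models the equal correlation holds on the link scale, not exactly on the observed scale, and nothing here shows the size of any error there. That limits the recommendation to continuous outcomes.

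**Conclusion.** The concern holds for the continuous secondary survey outcomes, as a conditional risk with no safeguard in the plan. If correlation decays with time, type I error for the baseline-to-18-month treatment contrast rises to about 7% under mild decay and 9-13% under autoregressive correlation of 0.5-0.9. Adjacent-wave contrasts become conservative, at about 4% and 2.6-1.4%. Single-wave arm differences are sound with complete data and equal variances, and nearly so with the random dropout examined. They reach about 8% at 18 months if the SD rises from 1.0 to 1.3.

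Every correlation, SD and dropout figure is assumed. A reader might also infer that the trial's main results are at risk. The documents do not support this: the primary outcomes are administrative totals from baseline to 18 months, not repeated survey scores. This should be corrected before analysis, but it does not threaten the primary comparison.

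**What to change.** In E.2, for continuous survey outcomes, replace alpha_i plus constant sigma^2 with an unstructured 4 x 4 within-person covariance across baseline, 6, 12 and 18 months. Keep the other terms. Base the tests and intervals for c_j and for beta + c_j on this model, and state which of the two is reported and which wave is the reference for c_j. Name a simpler fallback covariance structure in advance in case the model does not converge. Carry the same covariance into the Bayesian re-estimation in E.4.

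For binary and negative binomial survey outcomes, participant-clustered robust standard errors are at most a sensitivity analysis. The calculations here do not cover those models, and the random period intercepts shared by all participants mean that participants are not independent clusters within the model as written.

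The cost is SAP wording and a model option: 10 covariance parameters (4 variances and 6 covariances) instead of 2, estimated from about 450 families at up to four waves. No new data are needed.

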### D.3. Participant Characteristics

We will collect the following demographic and socioeconomic information from participants:

- Age
- Gender
- Self-reported race
- Self-reported ethnicity
- Number of adults in household
- Number of children in household
- Educational attainment
- Monthly income from employment
- Monthly income from other government benefits
- Employment
- Health Insurance Status (Insured versus uninsured)
- Child Health Insurance Status (If any child in home is uninsured)
- Housing status

In the event that there are high levels of missingness for any key covariate (i.e., >2%), multiple imputation methods will be used.

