### E.3. Subgroup analyses

Families involved with OCFS have varying levels of exposure to structural racism. Because of this we expect that treatment effects may vary as a function of participant race/ethnicity. We examine possible treatment heterogeneity by modifying our general regression model as follows:

$$\mu = E(y|T, X) = \alpha_i + \delta_j + \gamma_k + d_l(\beta T_i + c_j T_i) + \theta X_{ij}$$

where  $d$  is an interaction coefficient for participant race  $l$  on both the time-stable and time-varying components of the treatment effect.

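### The outcome models index the covariates by survey wave and nothing limits them to baseline, so the intent-to-treat models for the survey outcomes would, read literally, adjust for values measured after randomisation

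*Combined protocol and SAP*

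**What the plan says.** E.2 gives the general model with the treatment and covariate terms "\beta T_i + c_j T_i + \theta X_{ij}". It defines i as the participant and j as the survey period. The subgroup model in E.3 keeps the same covariate term: "d_l(\beta T_i + c_j T_i) + \theta X_{ij}".

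E.2 says that X "is a matrix of demographic characteristics" and that θ "is a vector of coefficients for demographic predictors". It does not list the items or say when they are measured. The average treatment effect is a contrast between arms at the same X: "ATE} = E(y|T = 1, X) - E(y|T = 0, X)". E.2 also states that the primary approach is intent-to-treat.

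The likely source of X is D.3, which opens with "We will collect the following demographic and socioeconomic information from participants" and lists 13 items, among them "Number of adults in household". D.1 says the survey covers "caretaker and child demographic, health, behavioral, educational, and social characteristics". It adds that everything is collected at baseline and that items able to change are asked again at each later wave. Section C places the first survey before treatment begins.

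The survey outcomes (secondary, D.2) are measured at baseline, 6, 12 and 18 months. The primary outcomes (D.2) are single totals from administrative records, running from baseline to 18 months.

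**The concern.** An intent-to-treat comparison should estimate the total effect of being assigned the cash. Adjusting for baseline covariates leaves that target intact. Adjusting for a covariate measured after the cash starts does not, if the cash can move the covariate. Part of the effect is then held fixed, and if the covariate and the outcome share unmeasured causes, a further distortion enters.

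How many items are at issue depends on what X contains. On the narrow demographic reading, two of the 13 D.3 items (numbers of adults and of children in the household) can change after randomisation in a way the cash might influence. If X draws on the whole D.3 list, six more join them: employment, two income items, two insurance items and housing status. Those are plausible channels for a monthly cash transfer.

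No planned check would expose the problem. The only sensitivity analysis (E.4) re-fits the same models with informative priors and so inherits X_ij.

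A related gap concerns the primary outcomes. As they are single totals, j has no meaning for them in X, in the wave intercepts or in c_j, and the formula does not say which X applies.

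**Working it through.** The plan states no figure on this point, so there is none to reproduce. The check is a reading of the text followed by an illustration.

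**Reading of the text**

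- Treatment is written T_i (person only), while the covariates are X_ij (person and wave).
- County is fixed at enrolment in E.2. X has no such limit.
- E.1 names baseline characteristics for the balance and attrition checks. E.2 and E.3 do not do so for the outcome models.
- D.1 provides repeat measurements of changeable items, so wave-specific values will be available.

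**Why the estimate moves**

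In a linear model with a separate treatment effect at each wave, the fitted model approximately satisfies, at wave j:

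arm difference in y = (β + c_j) + θ × (arm difference in X at wave j)

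Hence β + c_j ≈ total effect − θ × (change in X caused by the cash). With baseline X the arm difference is zero in expectation, because of randomisation, and the total effect is recovered.

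**Illustration in the E.2 layout (all inputs assumed)**

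Four waves, 400,000 participants (to show bias, not power), one third treated, person random intercept, wave intercepts and treatment-by-wave terms; county omitted. The covariate is number of adults (SD 0.67–0.69 in controls at 18 months; no floor imposed for negative shifts). The total effect is 0.25 and the outcome SD 1.00–1.12. Here b is the effect of one adult on the outcome and L the loading of unmeasured common causes. The 18-month effect adjusted for X_ij is:

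| Adults added per treated household | b=0, L=0 | b=0.1, L=0 | b=0.25, L=0 | b=0, L=0.3 | b=0.25, L=0.3 |
|---|---|---|---|---|---|
| +0.2 | 0.250 | 0.234 | 0.202 | 0.217 | 0.167 |
| +0.1 | 0.253 | 0.241 | 0.218 | 0.239 | 0.212 |
| 0 | 0.247 | 0.253 | 0.254 | 0.248 | 0.253 |
| −0.1 | 0.247 | 0.258 | 0.278 | 0.270 | 0.295 |
| −0.2 | 0.240 | 0.265 | 0.300 | 0.285 | 0.334 |

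Baseline-adjusted and unadjusted estimates were 0.240–0.256 throughout. X_ij-adjusted minus baseline-adjusted, in the same column order:

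- Shift +0.2: 0.00, −0.02, −0.05, −0.03, −0.08.
- Shift +0.1: 0.00, −0.01, −0.03, −0.02, −0.04.
- No shift: 0.00 in every column. Negative shifts mirror the positive ones.

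Check of the formula in the last column at +0.2: θ = 0.41 and shift = 0.203, so 0.41 × 0.203 = 0.083, which equals 0.250 − 0.167.

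**Second illustration at the planned size**

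150 versus 300, one post-baseline wave, 2,000 replicates, total effect 0.30, covariate SD 1 in controls. Here a is the effect of treatment on X, b the effect of X on the outcome and g the effect of an unmeasured common cause. Baseline adjustment averaged 0.295–0.303 in all 12 settings. Same-wave adjustment averaged:

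- 0.30 when a=0 or when b=g=0.
- 0.241 at a=0.2, b=0.3, g=0 (formula: 0.30 − 0.3 × 0.2 = 0.24).
- 0.183 at a=0.4, b=0.3, g=0 (formula: 0.30 − 0.3 × 0.4 = 0.18).
- 0.211 at a=0.4, b=0, g=0.3.
- 0.096 at a=0.4, b=0.3, g=0.3.

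**Scale**

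For an outcome SD of 1 and full follow-up, SE = √(1/150 + 1/300) = √0.0100 = 0.100. The non-zero shifts of 0.01 to 0.08 are therefore 0.01/0.10 = 0.1 to 0.08/0.10 = 0.8 of a standard error. At an outcome SD of 1.12 the SE is 0.112, and the largest shift is 0.083/0.112 = 0.74 of it.

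**The case against.** The strongest reply is that X_ij permits variation over waves without requiring it. Every row of a person-by-wave dataset is indexed ij, and a baseline value repeated across waves also fits the notation. The intent-to-treat statement, the baseline checks in E.1 and county at enrolment all lean that way. This stands as far as intent goes: the subscript does not prove that follow-up values are meant. It does not remove the defect. The same equation gives treatment a person-only index, and an analyst who follows it as printed would use wave-specific values.

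The contents of X are also unknown. If X is only age, gender, race and ethnicity, there is no problem. That is correct, and it is a reason to list the items. The count of two plus six items is a judgement. It leaves out educational attainment, which could also change, so it is if anything conservative.

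The illustration rests wholly on assumed inputs. Its top figure needs the largest value of each input at once, and it says nothing about the logit or negative binomial models. Attrition would raise the standard error and lower the ratio. All of this stands: the figures show a mechanism, not a measured consequence.

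Finally, the primary outcomes are not shown to be biased. That is agreed, and the severity does not rest on them.

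**Conclusion.** The concern holds. As printed, the intent-to-treat models for the survey outcomes adjust for post-randomisation values of any changeable item in X, and no text says otherwise. Confidence in this textual point is high.

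Whether it produces bias depends on three things the document leaves open: what X contains, whether the cash moves it, and whether it is linked to the outcome. Direction and size cannot be determined from the plan. Under the assumed inputs, the distortion from a single covariate is modest, at most about 0.8 of a standard error and zero in several settings. It does not shrink as the sample grows, and the full D.3 list would bring in more covariates. This should be fixed before analysis. For the primary outcomes the point is only that the formula does not specify which X applies.

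**What to change.** 1. In E.2 and E.3, replace X_ij with X_i and name the variables in X, saying which D.3 items are used.
2. State that X takes its values from the survey completed before treatment begins, in every intent-to-treat model and in the definition of the average treatment effect. Nothing is lost for age, because the wave intercepts absorb ageing between surveys.
3. For the cumulative administrative outcomes, write out a form of the model without j that uses the same X_i.
4. If any model with follow-up covariate values is run, label it exploratory and do not interpret it as the intent-to-treat effect.

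The cost is SAP wording only. D.1 already collects every variable at baseline, and section C puts that survey before treatment. If baseline values were always intended, the edit simply records that.
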